## **5.1 Recruitment Plan**

This study seeks a sample size of 600 patients. In order to accomplish this target the investigators plan to convert this study into a multicenter project, enlisting sites worldwide. At that time we anticipate we will have enough funding to cover the monitoring costs and thus anticipate accrual will increase as sites are added. In the meantime we plan to open the study at MDACC and LBJ and work toward our ultimate goal of an international, multicenter study.

## **6.0 REGISTRATION AND RANDOMIZATION**

All eligible patients in MD Anderson and LBJ will be required to provide informed signed consent before randomization. Randomization will be performed using the method with an equal allocation between the two treatment groups.

## **7.0 ADVERSE EVENTS**

### **7.1 Definitions**

The Investigator is responsible for reporting only common AEs (section 7.2) that are observed or reported during the study, regardless of their relationship to treatment or their clinical significance. Hematological and nonhematological AEs related to chemoradiation will not be collected due to the expectedness of the attribution (ie diarrhea, nausea, vomiting, etc.)

An AE is defined as any untoward medical occurrence in a patient enrolled into this study regardless of its causal relationship to study treatment.

A treatment-emergent AE is defined as any event not present prior to surgery or any event already present that worsens in either intensity or frequency following surgery.

All common AEs (section 7.2) that occur after surgery during the study must be reported in detail in the patient's source/chart and followed to satisfactory resolution or until the local Principal Investigator or Co-Investigator deems the event to be chronic or the patient to be stable. The description of the AE will include the onset date, date of resolution, severity, seriousness, , and the likelihood of relationship of the AE to study treatment.

Severity of adverse events will be graded using the National Cancer Institute Common Terminology Criteria for Adverse Events version 4.0 (CTC-AE v4.0),

If an adverse event occurs which is not contained in the CTC-AE v4.0, the five-point scale below will be used:

1. Mild: discomfort noticed but no disruption of normal daily activity.
2. Moderate: discomfort sufficient to reduce or affect daily activity.
3. Severe: inability to work or perform normal daily activity
4. Life Threatening: represents an immediate threat to life
5. Death

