### **1.2 Secondary Objectives**

- 1.2.1 To determine if patients with locally advanced cervical cancer have longer disease-free survival with pretherapeutic paraaortic surgical staging when compared to radiologic staging.
- 1.2.2 To determine short- and long-term morbidity of pretherapeutic surgical staging in patients with locally advanced cervical cancer
- 1.2.3 To determine sensitivity of pretreatment staging radiologic examinations in detecting metastatic disease.
- 1.2.4 To determine site of paraaortic metastatic disease along aorta as related to the inferior mesenteric artery (i.e. above or below) in patients with locally advanced cervical cancer
- 1.2.5 To evaluate surgical complication rates of the laparoscopic extraperitoneal paraaortic lymphadenectomy in a large cohort of patients.

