Currently, FDG-PET scanning is being utilized in attempts to better detect paraaortic lymph node spread. When combining four prospective studies that compared FDG-PET to gold standard surgical staging, Havrilesky et al. [7] found an overall sensitivity of 84% (95% CI 68-94%). Although this modality is an improvement over CT scan, it remains that 16% (and as high as 32%) of patients will be classified as node negative when in reality they have metastatic disease to their para-lymph nodes. The implications of undertreating these patients are disastrous, especially when one considers that the survival for patients with histologically positive paraaortic lymph nodes is as high as 50% if these metastases are detected and extended field radiation therapy is given [3,8].

The concept of surgical staging for patients with locally advanced cervical cancer has evolved over the last three decades. Surgical staging as a method of assessing lymph node status in patients with locally advanced cervical cancer may lead to a change in the radiation treatment plan in as many as 43% of patients [3]. Initially, patients were staged with traditional laparotomy and a transperitoneal approach. However, this led to a high complication rate from radiation effects on small bowel adhered to dissected areas in the pelvis. The description of the open extraperitoneal approach by Berman et al. [9] led to a sharp decrease in small bowel complications from radiation therapy [10]. Advances in endoscopic equipment and techniques have allowed for even less invasive approaches to lymph node dissection with laparoscopy either transperitoneally [6,11] or extraperitoneally [12-14]. Neither of these approaches appears to increase postoperative radiotherapy complications when surgeries are limited to lymph node dissection only. These procedures do not significantly delay definitive therapy as patients typically go on to receive their radiotherapy 7-10 days following laparoscopic staging.

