### Analysis

We will use descriptive statistics to summarize patient demographic and clinical characteristics by treatment group.

We will estimate overall survival (OS) with the product limit estimator of Kaplan and Meier [19], and we will estimate the 3-year OS with a 95% confidence interval. We will also estimate the median OS with a 95% confidence interval. We will use the log-rank test to compare the 2 treatment groups with respect to OS.

We will also use the log-rank test for the interim analysis of OS, which will take place after 131 deaths have been observed. If the p-value from this test is  $< 0.0031$  the study will be stopped for efficacy, and if the p-value from this test is  $> 0.3217$  the study will be stopped for futility.

We will use Cox [20] proportional hazards regression to model OS as a function of treatment and other well-known and potential prognostic factors such as clinical stage, histology, and grade. We will estimate the hazard ratio for treatment (preoperative paraaortic surgical staging vs not) and other potential prognostic factors with 95% confidence intervals.

We will perform similar analyses for disease-free survival (DFS) as for OS.

We will tabulate the numbers of patients with particular short- and long-term morbidities including intraoperative and postoperative complications and treatment delay for each treatment group, and we will use the chi-square test to compare treatment groups with respect to the incidence of these morbidities.

For the treatment arm with pretreatment paraaortic surgical staging we will estimate the sensitivity of pretreatment radiologic staging examinations to detect metastatic disease with a 95% confidence interval. The findings of the pretreatment paraaortic surgical staging will be considered the true diagnosis of metastatic disease.

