#### **7.5 Adverse Event Reporting**

Information regarding AEs will be collected from the time the patient signs the informed consent form up to 6 months post treatment.

All AEs reported or observed during the study will be recorded as an AE in the patient's source/chart. Information to be collected includes:

- Type of event
- Onset
- Investigator-specified assessment of severity and relationship to treatment
- Resolution of the event
- Grade
- Any required treatment or evaluations

Adverse events resulting from concurrent illnesses, reactions to concurrent illnesses, reactions to concurrent medications, or progression of disease states must also be recorded. All AEs will be followed to adequate resolution. Any medical condition that is present at the time that the patient is screened but does not deteriorate should not be

reported as an AE. However, if it deteriorates at any time during the study it should be recorded as an AE.

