## 7.7 Assessment of Causality

The Investigator's assessment of an AE's relationship to treatment is part of the documentation process, but it is not a factor in determining what is or is not reported in the study. If there is any doubt as to whether a clinical observation is an AE, the event should be reported.

The relationship or association of the test article in causing or contributing to the AE will be characterized using the following classification and criteria:

- **Unrelated:** This relationship suggests that there is no association between the surgery and the reported event.
- **Possible:** This relationship suggests that treatment caused or contributed to the AE, i.e. the event follows a reasonable temporal sequence from the time of surgery and/or follows a known response pattern to the surgery, but could also have been produced by other factors.
- **Probable:** This relationship suggests that a reasonable temporal sequence of the event with drug administration exists and the likely association of the event with the surgery. This will be based upon the known or previously reported complications to the surgery, or judgment based on the Investigator's clinical experience.
- **Definite:** This relationship suggests that a definite causal relationship exists between the surgery and the AE, and other conditions (concurrent illness, progression/expression of disease state, or concurrent medication reaction) do not appear to explain the event.

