## **9.0 STUDY COMMITTEES**

### **9.1 Trial Safety Committee (TSC)**

An independent Trial Safety Committee (TSC) will be assembled to review the safety and efficacy data collected during the study. They will be composed of individuals who

are independent of the study and are not involved (either directly or indirectly) in the management of this study. The membership includes the following:

- 3 gynecological oncologists who are otherwise not related to the trial;
- 2 Statisticians who are otherwise not related to the trial;
- 1 public member

The TSC will be responsible for monitoring, on an ongoing basis, any of the following events:

- General Toxicity (NCI-CTC AE, v4.0): grade 3 and grade 4 adverse events, serious adverse events
- A patient death (grade 5)

The first safety analysis will be performed after 20 patients have completed treatment. All further TSC reviews should take place twice per year and the committee will review all safety data collected during the study.

Following each meeting, the committee will recommend that the study continues according to the protocol or may suggest changes to the protocol based on the outcome of the data review. In exceptional cases the committee may recommend stopping the study due to safety reasons.

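### Section 7.1 excludes chemoradiation-related adverse events, contrary to the plan's other reporting rules, and so leaves non-serious, unlisted toxicity of the tested strategy uncollected

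*Combined protocol and SAP*

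**What the plan says.** Section 7.1 makes the investigator responsible for "reporting only common AEs (section 7.2) that are observed or reported during the study, regardless of their relationship to treatment". The next sentence states that "Hematological and nonhematological AEs related to chemoradiation will not be collected due to the expectedness of the attribution", with diarrhea, nausea and vomiting as examples. The same section defines treatment-emergent events, and sets the duty to report listed events in detail, by reference to the time after surgery. The list in 7.2 is headed as postoperative. It includes items that radiation could also cause, such as fistula, prolonged ileus, bladder dysfunction and lymphoedema.

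Other sections read differently. Section 7.5 says "All AEs reported or observed during the study will be recorded as an AE", with collection running to 6 months after treatment. Section 7.7 says of the causality assessment that "it is not a factor in determining what is or is not reported in the study". The reporting requirements under 7.4 cover serious events whether or not related to surgery, until 30 days after primary therapy. Section 9.1 gives the Trial Safety Committee "General Toxicity (NCI-CTC AE, v4.0): grade 3 and grade 4 adverse events, serious adverse events", as well as deaths, with no exception for chemoradiation.

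Objective 1.2.2 is "To determine short- and long-term morbidity of pretherapeutic surgical staging in patients with locally advanced cervical cancer". For it, the Analysis part of section 5.0 tabulates short- and long-term morbidities by arm and adds that "we will use the chi-square test to compare treatment groups with respect to the incidence of these morbidities".

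**The concern.** Leaving out expected background toxicity is reasonable when the background treatment is the same in both arms. Here it is not. Under section 4.0, experimental-arm women found to have positive paraaortic nodes go on to extended-field radiotherapy, while the standard arm is assigned a pelvic field. Any extra toxicity of the larger field is a consequence of the strategy under test, yet section 7.1 files it under chemoradiation and does not collect it. Section 2.0 shows that the interaction of surgery and radiation was a known issue: of early transperitoneal staging by laparotomy it says "this led to a high complication rate from radiation effects on small bowel adhered to dissected areas in the pelvis".

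At stake are the morbidity comparison for objective 1.2.2 and the committee's ability to see grade 3 and 4 toxicity while the trial runs. Sites also cannot obey 7.1, 7.5 and 7.7 together, so what is collected may depend on which section a site follows.

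**Working it through.** **1. What is captured when 7.1 is followed as written.** Take an event attributed to chemoradiation:

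| Type of event | Status |
|---|---|
| On the 7.2 list | Kept by the first sentence of 7.1 (any relationship); put in doubt by the second |
| Serious, up to 30 days after primary therapy | Reported under 7.4, related to surgery or not |
| Serious, unlisted, after 30 days | Not secured: outside the SAE window and excluded by 7.1 |
| Non-serious and unlisted, including grade 3 | Not collected under 7.1; collected if 7.5, 7.7 or 9.1 governs |

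The last row is the firm gap. The conflict between rules is explicit there.

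**2. How many women it concerns.** Inputs from section 5.0: 600 patients, equal allocation, about 79% truly node-negative and 21% with false-negative imaging. These shares reproduce the plan's 3-year survival figures:

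- standard arm: 0.79 × 0.75 + 0.21 × 0.10 = 0.6135 (plan: 61%)
- experimental arm: 0.79 × 0.75 + 0.21 × 0.50 = 0.6975 (plan: 70%)

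The design therefore rests on 21% of the experimental arm receiving the extended field: 0.21 × 300 = 63 women. With the 22% quoted in section 2.0 it is 66.

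**3. What collection would and would not achieve.** The plan states no power for morbidity and gives no toxicity rates, so the rates here are assumed. An excess of x points among extended-field patients becomes 0.21x at arm level. With 300 per arm and two-sided 0.05, power is approximately Φ[(Δ − 1.96·SE0)/SE1], where SE0 = √(2p̄(1−p̄)/300) and SE1 = √([p0(1−p0) + p1(1−p1)]/300). Example: p0 = 0.20 and x = 40 points give p1 = 0.284, SE0 = 0.0350, SE1 = 0.0348, and (0.084 − 0.0685)/0.0348 = 0.44, so power is 67%.

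| Excess in extended-field patients | Arm difference | Power, 10% background | 20% | 30% | 20%, half of events kept |
|---|---|---|---|---|---|
| 10 points | 2.1 | 13% | 9% | 8% | 6% |
| 20 points | 4.2 | 35% | 24% | 20% | 13% |
| 30 points | 6.3 | 63% | 45% | 37% | 23% |
| 40 points | 8.4 | 84% | 67% | 58% | 35% |

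If none of these events is kept, the observable difference is zero. Collection is thus necessary, but the arm-level test alone is weak except for large excesses. A description by field received is needed beside it.

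**4. Attribution.** If 7.2 events are kept whatever their cause, attribution has no effect on them. If sites filter them by cause, the result depends on retention rates that the documents do not give. With equal true rates in both arms, the same formula gives these rejection rates for assumed recorded rates: 8% vs 9%, about 6%; 5% vs 7%, about 18%; 2% vs 6%, about 71%; 0% vs 5%, about 98%. A range this wide shows sensitivity to the assumption. It is not an estimate.

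**The case against.** The strongest reply is that the two sentences of 7.1 can be read together: listed events are always reported, and only unlisted, expected toxicity is dropped. The examples given fit that reading. Fistula, ileus, bladder dysfunction and lymphoedema would then be counted in both arms, and serious events arrive through 7.4. Objective 1.2.2 concerns the morbidity of surgical staging, and the Analysis part names intraoperative and postoperative complications and treatment delay, which focused collection largely serves. Section 2.0 also says that the laparoscopic approaches do not appear to increase radiotherapy complications when limited to node dissection. Finally, 7.5 keeps all events in the chart, so some could be retrieved later.

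Most of this stands, and it rules out two stronger readings that a reader might infer. One is that extended-field toxicity goes wholly uncollected and the safety committee cannot see it. The 7.2 list, the SAE rule and the committee's access to serious events and deaths contradict that. The other is that the morbidity comparison is biased by unblinded attribution. That requires 7.2 events to be filtered by cause, against the first sentence of 7.1 and against 7.7. Blinding is not mentioned, and open-label treatment is a sound inference because no sham surgery is described, but differential attribution is not shown.

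The reply does not close the gap for non-serious, unlisted events. Chart entries are not study data graded alike in both arms, and the committee needs the events during the trial. That laparoscopic staging adds no radiotherapy complications is something a randomized trial should check.

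**Conclusion.** The point holds in a limited form. Section 7.1 contradicts its own preceding sentence and sections 7.5, 7.7 and 9.1. If it governs, non-serious, unlisted chemoradiation toxicity is lost, in a trial where about 63 of 300 experimental-arm women are planned to receive a larger field than the standard arm. The figure of 63 assumes full accrual and the phase II share. The radiotherapy text also allows for paraaortic treatment with positive common iliac nodes without naming an arm, so the contrast in practice may be smaller.

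Attribution that differs by arm is a risk, and its net direction is open. Dropping extended-field toxicity favours the surgical arm. Calling the same event surgical in one arm and radiation-related in the other counts against it. No false-positive rate should be quoted as an estimate.

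This should be fixed because a secondary objective and safety oversight depend on it. The primary overall survival analysis is unaffected. The 6-month AE window separately limits what can be said about long-term morbidity, and the change below does not cure that.

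**What to change.** Replace both the exclusion sentence and the limit to common events in 7.1 with one rule for both arms that does not depend on attribution. Deleting the exclusion alone is not enough, because the limit and the surgery-based trigger would remain.

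- Record the 7.2 events and grade 3 or higher CTCAE v4.0 gastrointestinal, genitourinary and clinically relevant hematological toxicity. Word the hematological part to agree with the laboratory rule in 7.3.
- Count onset from randomization instead of surgery, which the standard arm does not have.
- Align 7.5, 7.7 and 9.1 with this rule.
- In the Analysis part of section 5.0, compare arms on events irrespective of attribution and add a descriptive split by radiation field received. Because the field follows from the nodal findings, that split is not a randomized comparison.
- Report intraoperative and wound events descriptively for the surgical arm only.

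The cost is amendment wording, some added case-report-form entries and modest extra data entry at visits already scheduled. No added patients or procedures are needed.

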## **7.2 Common Adverse Events**

The most common postoperative adverse events from study treatment include:

- Intraoperative injury (bowel, bladder, ureter, nerves or blood vessels)
- Wound complication (vault or pelvic hematoma or collection)
- Infectious complications (bladder, chest, septicemia)
- Postoperative hemorrhage/ bleeding, thromboembolic events (DVT, pulmonary embolus)
- Prolonged Ileus > 7 days, fistula formation (any) or hernia formation
- Cardiac, pulmonary renal or cerebrovascular complications
- Returned to theatre in same admission (re-operation)
- Bladder dysfunction
- Lymphoedema

## **7.3 Laboratory Test Abnormalities**

Laboratory test value abnormalities will not be reported as AEs, unless there is an associated clinical condition for which the patient is given treatment, concomitant treatment is altered or the event is considered a serious adverse event.

#### **7.4 Serious Adverse Events**

An SAE is defined as any event that:

- Results in death
- Is immediately life threatening
- Requires inpatient hospitalization or prolongation of existing hospitalization
- Results in persistent or significant disability/incapacity
- Is a congenital anomaly/birth defect.

Important medical events that may not result in death, be life-threatening, or require hospitalization may be considered an SAE when, based upon appropriate medical judgment, they may jeopardize the patient and may require medical or surgical intervention to prevent one of the outcomes listed in this definition.

#### **Reporting requirements:**

Any AE considered serious or which meets the previous criteria must be reported to the study chair within one business day from the time that study personnel first become aware of the serious adverse event.

All reported SAEs (related or not to the surgery) will be followed until satisfactory resolution or until the attending physician deems the event to be chronic or the patient to be stable. SAEs will be reported till 30 days from completion of primary therapy.

#### **7.5 Adverse Event Reporting**

Information regarding AEs will be collected from the time the patient signs the informed consent form up to 6 months post treatment.

All AEs reported or observed during the study will be recorded as an AE in the patient's source/chart. Information to be collected includes:

- Type of event
- Onset
- Investigator-specified assessment of severity and relationship to treatment
- Resolution of the event
- Grade
- Any required treatment or evaluations

Adverse events resulting from concurrent illnesses, reactions to concurrent illnesses, reactions to concurrent medications, or progression of disease states must also be recorded. All AEs will be followed to adequate resolution. Any medical condition that is present at the time that the patient is screened but does not deteriorate should not be

reported as an AE. However, if it deteriorates at any time during the study it should be recorded as an AE.

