#### **4.0 THERAPEUTIC PROGRAM**

This Phase III randomized study is designed to determine if patients with locally advanced cervical cancer have longer overall survivals with pretherapeutic paraaortic surgical staging when compared to radiologic staging.

All eligible patients in MD Anderson and Lyndon B. Johnson General Hospital (LBJ) will be required to sign an informed consent prior to randomization. Patients will be equally allocated between the 2 treatment groups.

Eligible patients will be randomized to either standard chemoradiation (standard-of-care arm) or pretherapeutic paraaortic lymphadenectomy followed by tailored chemoradiation (experimental arm). Pretherapeutic lymphadenectomy will be performed via the laparoscopic extraperitoneal approach using either traditional laparoscopy or robotically-assisted laparoscopy. Patient demographic and treatment information will be collected at time of enrollment and throughout initial definitive therapy (Appendix C).

*Radiology Protocol and Definitions of Positive and Indeterminate Nodes*

All scans will be performed on a dedicated Positron Emission Tomography/Computed Tomography (PET/CT) scanner that will allow fusion of PET and CT images. Standard imaging protocols for PET/CT will be followed with non-contrast CT used for attenuation correction.

The standard definition of abnormal lymph nodes in the abdomen and pelvis by cross sectional imaging is size greater than 10 mm. Therefore nodes greater than 10 mm in the abdomen or pelvis will be considered abnormal by CT.

PET/CT images will be evaluated qualitatively for focal areas of abnormally increased 18-fluorine fluorodeoxy glucose (FDG) uptake. A positive finding is defined as the presence of abnormal FDG uptake when accumulation of the tracer is moderately to markedly increased relative to the uptake in comparable normal structures or surrounding tissues, with the exclusion of physiologic bowel and urinary activity. A negative finding is defined as no detectable FDG uptake.

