If the paraaortic nodes for patients with positive common iliacs are treated, then PTV must end at the top of L2; for patients with positive paraaortic nodes, the PTV must end at the top of T12 (therefore, the CTV must end several slices below these endpoints). The top of the field should be at least one vertebra above the highest positive node. Bowel – will be outlined on every slice, including up to 2 cm above the planning target volume and no more. It includes the volume surrounding loops of small bowel out to the edge of the peritoneum because the bowel may lie within this space at any time throughout the course of treatment.

The dose constraints for critical structures are as follows:

- Bowel:  $\leq 30\%$  to receive  $> 40$  Gy
- Rectum:  $\leq 60\%$  to receive  $> 45$  Gy
- Bladder:  $\leq 35\%$  to receive  $> 45$  Gy
- Kidneys: 2/3 of each kidney to receive  $\leq 18$  Gy
- Spinal cord: no more than 45 Gy at any point with a volume of 0.03 cc or greater

*Follow-Up/Surveillance:*

A PET scan will be obtained at 3 months after completion of chemoradiation therapy. CT scans will be obtained every 6 months for the next three years thereafter. Follow-up surveillance of patients will consist of serial clinical examinations by an oncologist every 3 months for the first 2 years, every 6 months for the next 3 years and annually thereafter. Patients will come off study at 5 years after completion of initial chemoradiation therapy or at time of death.

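### Adverse event collection ends 6 months post treatment, so morbidity with later onset falls outside the planned short- and long-term comparison of the arms

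*Combined protocol and SAP*

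**What the plan says.** Objective 1.2.2 is "To determine short- and long-term morbidity of pretherapeutic surgical staging in patients with locally advanced cervical cancer". It names no comparison. The comparison is in section 5.0, Analysis, which tabulates short- and long-term morbidities by treatment group and adds that "we will use the chi-square test to compare treatment groups with respect to the incidence of these morbidities".

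Section 7.5 sets the collection period: "Information regarding AEs will be collected from the time the patient signs the informed consent form up to 6 months post treatment". Neither long-term nor post treatment is defined.

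Section 4.0, Follow-Up/Surveillance, schedules examinations "every 3 months for the first 2 years, every 6 months for the next 3 years and annually thereafter", and states: "Patients will come off study at 5 years after completion of initial chemoradiation therapy or at time of death".

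Sections 7.1 and 7.5 require recorded events to be followed until they resolve; 7.1 also allows follow-up to end once the event is judged chronic or the patient stable. Sections 7.1 and 7.5 speak of events during the study, and 7.6 has patients questioned at each study visit. None of these gives an end date. Section 7.1 dates treatment-emergent events, and the duty to chart section 7.2 events in detail, from surgery.

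**The concern.** The experimental arm adds an operation to chemoradiation, so late harm is part of how any survival gain would be judged. The plan promises a long-term morbidity result and sees patients for 5 years, yet its one stated window closes after 6 months. Several events listed in section 7.2 can begin later than that, and no rule says that they are then recorded. If section 7.5 is followed, the table labelled long-term contains only events that began early. If the arms differ only in late onsets, the chi-square test has nothing to detect.

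A secondary point is that the standard arm has no staging operation, so the surgery-based wording in section 7.1 cannot be applied there as written.

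**Working it through.** The plan gives no sample size, event rate or power for the morbidity comparison, so there is no figure of its own to reproduce.

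**1. Visits inside and outside the window** (section 4.0 against section 7.5, counting from the end of chemoradiation).
- Years 1–2: 24/3 = 8 visits. Years 3–5: 36/6 = 6 visits. Total 14.
- Inside 6 months: months 3 and 6. Outside: 14 − 2 = 12.
- In time, the window covers 6/60 = 10% of the 5 years.

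**2. Patients still under observation when the window closes.** Section 5.0 gives 600 patients, equally allocated, with 3-year survival of 61% and 70%. Assume exponential survival and a lag L of 0 to 0.3 years from randomisation to the end of treatment.
- Hazards: −ln(0.61)/3 = 0.1648 and −ln(0.70)/3 = 0.1189 per year.
- Alive at 6 months: 300·exp(−hazard × (0.5 + L)) in each arm.
- L = 0: 276 + 283 = 559. L = 0.3: 263 + 273 = 536.

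So about 536 to 559 of 600 patients would be alive and able to have a late-onset event.

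**3. Illustration of what could be lost.** All event rates here are assumed, and every patient is taken as observed for 5 years.
- A section 7.2 event with 10% 5-year risk in both arms gives 600 × 0.10 = 60 onsets. If 75%, 50% or 25% begin by month 6, then 15, 30 or 45 are missed.
- Suppose true 5-year risks of 10% and 18%, 300 patients per arm, a two-sided pooled chi-square test at 0.05 (exact binomial enumeration), and the same share recorded in each arm:

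| Share of onsets recorded | Risks seen by the test | Power |
|---|---|---|
| 100% | 10% vs 18% | 81% |
| 75% | 7.5% vs 13.5% | 68% |
| 50% | 5% vs 9% | 49% |
| 25% | 2.5% vs 4.5% | 26% |

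**4. Entries needed to close the gap.** The 12 later visits are at months 9, 12, 15, 18, 21, 24, 30, 36, 42, 48, 54 and 60. Expected entries per arm are the sum over these months m of 300·exp(−hazard × (L + m/12)).
- All patients followed for 5 years: 2,419 + 2,689 = 5,108 (L = 0); 2,302 + 2,595 = 4,897 (L = 0.3).
- Follow-up ending at the planned 7.6 years (section 5.0), with uniform accrual over 5 years: each term is multiplied by min(1, (7.6 − L − m/12)/5). This gives about 4,650 (L = 0) and 4,340 (L = 0.3).
- In the second case, the share of patients enrolled early enough to reach 5 years is (7.6 − 5)/5 = 52% (L = 0) or (7.6 − 5.3)/5 = 46% (L = 0.3).

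**The case against.** The best defence is that other wording extends the window. Sections 7.1 and 7.5 refer to the study as a whole, section 7.6 has a question at each visit, and section 8.0 provides for continued monitoring of toxicity after withdrawal. None of these sets a period, so they conflict with section 7.5 and do not replace it. Follow-up to resolution does cover persistent events that begin early, and that part of the defence stands. Long-term might also have been meant as 6 months, but nothing says so. Appendix C is not in the text available; section 4.0 describes it as covering enrolment and initial definitive therapy.

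It is also fair that the morbidity comparison has no power target, that every event rate used above is assumed, and that some section 7.2 events, such as intraoperative injury or same-admission re-operation, cannot begin late.

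Some stronger readings are tempting but unsupported:
- **The window has no end in the standard arm.** This takes post treatment to mean after surgery, because section 7.2 says "The most common postoperative adverse events from study treatment include". The reading is strained: section 4.0 defines both arms as including chemoradiation, and section 7.4 dates from the completion of primary therapy.
- **Events are under-recorded in one arm.** Section 7.1 exempts chemoradiation-related events, but its examples are diarrhoea, nausea and vomiting, none of them in section 7.2. The sentence before it requires section 7.2 events to be reported "regardless of their relationship to treatment or their clinical significance", and section 7.7 says that causality does not decide reporting. The documents establish neither the size nor the direction of any imbalance.
- **Serious late events or safety committee data go missing.** A serious section 7.2 event after the 30-day limit in section 7.4 is still an adverse event within the 6-month window, and section 9.1 gives the committee all safety data collected.

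**Conclusion.** The concern holds for new-onset section 7.2 events after month 6, in both arms. Counting post treatment from the end of chemoradiation, 12 of 14 scheduled visits lie outside the collection window, at a time when most patients are expected to be alive. As written, the plan cannot deliver the late part of objective 1.2.2 or of the section 5.0 comparison, and a real late difference could be reported as no difference.

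The visit count rests only on the documents. The number alive also needs exponential survival and the assumed lag. The missed-onset and power figures depend on assumed risks and on full 5-year observation of all 600 patients, so they show what could happen and are not estimates for this trial. The surgery-based wording in section 7.1 is a secondary point of wording. The matter concerns one secondary objective, leaves the overall survival test untouched, and should be corrected because the remedy is cheap.

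**What to change.** **(a) Window and analysis.** Amend section 7.5 so that new-onset section 7.2 events are recorded in both arms at the visits already scheduled, to 5 years after completion of chemoradiation or the end of study follow-up. Date both post treatment and long-term from that completion in both arms. Because follow-up will differ between patients, summarise late events by cumulative incidence with death as a competing event, and keep chi-square for the fixed short-term window. If collection is not extended, take long-term out of the section 5.0 comparison and state that it covers onsets to 6 months only.

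**(b) Section 7.1.** Replace the surgery anchor with a common origin such as randomisation, and add that the chemoradiation exemption does not remove section 7.2 events.

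**Cost.** A protocol amendment, a case report form change, and a section 7.2 checklist at up to 12 existing visits per patient: about 4,340 to 4,650 entries if follow-up ends at 7.6 years, or 4,900 to 5,100 if everyone is followed for 5 years. No new visits or procedures are needed. The fallback in (a) and item (b) are wording changes only, but the fallback gives up part of objective 1.2.2.
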